7.4.2 Analysis of Secondary Endpoints

Similar analysis of the primary endpoint as described in Section 7.4.1 will also be conducted on the secondary endpoint PFS.

PFS is defined as the time from the date of randomization until the date of disease progression (radiographic progression) per RECIST 1.1, or death from any cause on study, whichever occurs first.

The following subjects will be censored at the date of the last radiological assessment showing no progression:

- 1) subjects who initiated another anti-tumor therapy before documented PD or death,
- 2) subjects who progressed or died after missing two or more consecutive radiological assessments.

Subjects are considered to have missed two or more consecutive radiological assessments if duration between two consecutive imaging scans are more than 20 weeks while on treatment. Subjects who have no valid post-baseline tumor assessment will be censored at day 1.

The distribution of PFS will be estimated for each treatment group using Kaplan-Meier methodology and compared between the Enzalutamide and placebo treatment groups using the stratified log-rank test. Stratification will be done by the regions (Asia versus Other) and ECOG performance status (0 versus 1). Additionally, unstratified analysis will be performed as well.

A sensitivity analysis for subjects randomized and treated will be performed if needed, depending on number of patients randomized and not treated, this will be decided at the Final Data Review if this analysis is needed or not.

A sensitivity analysis will be done if needed with similar PFS definition, and the initiation of another anti-tumor therapy will be considered as an event, and evidence of progression could come from two sources: radiographical or clinical. This sensitivity analysis will be performed only if further investigation is needed.

7.4.3 Analysis of Exploratory Endpoints

7.5 Analysis of Safety

Safety will be assessed on an ongoing basis by physical examination, measurement of vital signs, laboratory assessments, 12-lead ECGs, and evaluation of TEAEs/serious TEAEs.

Safety analyses will be conducted using the SAF. The SAF is defined as all subjects who have initiated at least 1 or partial capsule of study drug. The treatment emergent period will be defined as the period of time from the first dose date of study drug to 30 days after the last dose date of study drug or the start of subsequent treatment (whichever is first). Only data within this period will be summarized in safety analysis. Safety will be assessed through descriptive statistics for the frequency of adverse events by system organ class (SOC), preferred term (PT), and NCI CTCAE grade, the frequency of treatment discontinuations due to adverse events, vital signs, ECG, and laboratory evaluations.

All safety summaries will be provided using the SAF population.

7.5.1 Adverse Events

The severity of all adverse events is to be evaluated by the Investigator based on the NCI CTCAE, version 4.03. All adverse events will be coded to preferred term and system organ class using Medical Dictionary for Regulatory Activities (MedDRA). The number and percentage of subjects with treatment emergent adverse events will be presented by MedDRA system organ class and preferred term, relationship to study treatment, and NCI CTCAE grade. A subject reporting the same adverse event more than once is counted once and at the maximum severity or strongest relationship to study drug treatment, when calculating incidence.

The coding dictionary for this study will be MedDRA. It will be used to summarize AEs by SOC and PT.

An overview table will include the following details:

- Number of TEAEs,
- Number and percentage of subjects with TEAEs,
- Number of drug related TEAEs,
- Number and percentage of subjects with drug related TEAEs,
- Number of serious TEAEs,
- Number and percentage of subjects with serious TEAEs,
- Number of serious drug related TEAEs,
- Number and percentage of subjects with serious drug related TEAEs,
- Number of TEAEs leading to withdrawal of treatment,
- Number and percentage of subjects with TEAEs leading to withdrawal of treatment,
- Number of drug related TEAEs leading to withdrawal of treatment,

- Number and percentage of subjects with drug related TEAEs leading to withdrawal of treatment,
- Number of TEAEs leading to death,
- Number and percentage of subjects with TEAEs leading to death,
- Number of drug related TEAEs leading to death,
- Number and percentage of subjects with drug related TEAEs leading to death, and
- Number and percentage of subjects with death.

The number and percentage of subjects with TEAEs, as classified by SOC and PT will be summarized. Summaries will be provided for:

- TEAEs
- drug related TEAEs,
- serious TEAEs,
- grade 3 or higher TEAEs.
- drug related serious TEAEs,
- TEAEs leading to withdrawal of treatment,
- drug related TEAEs leading to withdrawal of treatment,

TEAEs and the number and percentage of subjects with TEAEs, as classified by SOC and PT will also be summarized by grade and by relationship to study drug. If an adverse event changes in grade or relationship, then the subject will be counted only once with the maximum grade and highest degree of relationship. The adverse event however will be presented in each category they were classified to. If a subject has an event more than once with missing grade/relationship and with non-missing grade/relationship, then the subject will be counted as missing grade/relationship. Drug related TEAEs will be presented in a similar way by grade only.

The Always Serious Terms List is a list of AEs that a Sponsor determines regardless of Investigator assessment are to be captured as serious. Serious TEAEs table will include both investigator reported and Astellas upgraded ones according to Always Serious Terms List. In the listing they will be presented with different flag.

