5 TREATMENTS AND EVALUATION

5.1 Dosing and Administration of Study Drug(s) and Other Medication(s)

5.1.1 Dose/Dose Regimen and Administration Period

Eligible subjects will receive enzalutamide 160 mg/day (4 x 40 mg capsules) or placebo until disease progression, unacceptable toxicity, or any other discontinuation criteria are met. Best supportive care will be given to all subjects in addition to study drug. Best supportive care may include medications and supportive measures deemed necessary per Investigator's discretion to palliate disease-related symptoms and improve quality of life. Subjects on strong CYP2C8 (e.g., gemfibrozil) inhibitor should start study drug at 80mg/day after consultation with the Medical Monitor, if coadministration cannot be avoided.

Study drug will be self-administered at home by the subject, except for visit days where pharmacokinetic samples are collected. On visit days with pharmacokinetic sampling, study drug will be administered in clinic after the pharmacokinetic sample is collected. Subjects will keep a diary to record the date and time of study drug dose on the 2 days before pharmacokinetic visit days.

Subjects should not make up missed or vomited doses; dosing should resume on the next calendar day unless otherwise instructed. For the purposes of this study, a “missed dose” is considered a dose not administered within 4 hours of the regular dosing time.

Subjects may take study drug with or without food. Subjects must swallow capsules whole. Study drug may not be chewed, dissolved or capsules opened.

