7.1 Sample Size

This sample size was primarily determined to provide sufficient clinical experience to support the design of later-stage clinical development, such as phase 3 studies.

Sample size calculations were performed using EAST 5 software based on the following assumptions:

- 2:1 randomization for enzalutamide vs placebo.
- Median OS for placebo and enzalutamide are 7.0 months and 10.77 months (HR=0.65), respectively.
- A study enrollment period of 18 months and a total study duration of 27 months.

With 109 death events, the study can achieve 80% power to detect a statistically significant difference using 1-sided log-rank test with 10% level of significance. Assuming no loss to follow-up, approximately 144 subjects were originally planned to reach this number of events.

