7.5 Analysis of Safety

7.5.1 Adverse Events

Safety will be assessed through descriptive statistics for the frequency of TEAEs by system organ class, preferred term, and the NCI CTCAE grade, the frequency of treatment discontinuations due to AEs, vital signs, ECG and laboratory evaluations.

The severity of all AEs is to be evaluated by the Investigator based on the NCI CTCAE, version 4.03. All AEs will be coded to preferred term and system organ class using MedDRA. The number and percentage of subjects with TEAEs will be presented by MedDRA system organ class and preferred term, relationship to study treatment, and NCI CTCAE grade. TEAE is defined as an AE observed during the treatment-emergent period, which is from the first dose date of study drug to 30 days after the last dose date of study drug or the start of subsequent treatment, whichever is first. A subject reporting the same AE more than once is counted once and at the maximum severity or strongest relationship to study drug treatment, when calculating incidence.

The number and percentage of TEAEs, serious TEAEs, AEs leading to discontinuation and TEAEs related to study drug will be summarized by system organ class, preferred term and treatment group. The number and percentage of TEAEs by severity will also be summarized. All AEs will be listed.

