3.2 Study Design

This is a multicenter, randomized, double-blind, placebo-controlled phase 2 study evaluating the efficacy, safety, and tolerability of enzalutamide monotherapy in approximately 144 subjects in Europe, Asia and North America with HCC of any etiology who have progressed on or were intolerant to sorafenib or other anti-VEGF therapy in the advanced setting. Each region will have no more than 70% of overall subjects enrolled. Enrollment may be limited by the sponsor in any region or country in order to have representation of the patient populations from all 3 regions as there may be a difference in responses to treatment or tolerability.

The study will consist of a Screening Period, Treatment Period and a Follow-up Period. Eligible subjects will be stratified by geographic region (Asia versus other) and Eastern Cooperative Oncology Group (ECOG) performance status (0 versus 1) and randomized in a 2:1 ratio to receive enzalutamide 160 mg/day or placebo until disease progression, unacceptable toxicity, or any other discontinuation criterion is met. Study evaluations will occur as specified in the Schedule of Assessments.

An end of treatment visit will be performed within 7 days of the last dose of study drug. Upon discontinuation of treatment for any reason, subjects will enter the follow-up period. A

follow-up visit will be performed approximately 30 days after the last dose of study drug. All Adverse Events (AEs) that occur during the safety reporting period (from the first dose of study drug through 30 days after the last dose of study drug or initiation of a new antineoplastic or new investigational agent, whichever occurs first) are to be followed up until resolved or judged to be no longer clinically significant, or until they become chronic to the extent that they can be fully characterized. This may be performed by telephone if applicable. Long-term follow-up visits will be conducted every 30 days for up to 2 years to collect information on survival and subsequent therapies.

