7.3 Study Drugs

7.3.1 Exposure

The following information on drug exposure will be presented for the SAF:

- Descriptive statistics for cumulative amount of the drug a subject was exposed to and average daily dose; and
- Number and percent of subjects with dose increase, decreases or interruptions.

Duration of exposure (defined in days as the date of last dosing - the date of first dosing + 1) will be summarized in two ways.

- Descriptive statistics will be presented.
- Exposure time will be categorized according to the following categories by study drug:
 - less than 3 months
 - at least 3 months and less than 6 months
 - at least 6 months

Counts and percentages of subjects in each of these categories will be summarized for the SAF.

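### Adverse event tables give only unadjusted counts and percentages, although time at risk varies; exposure-adjusted rates should be added beside them

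*SAP*

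**What the plan says.** **Adverse event tables.** SAP 7.5.1 plans the tables by system organ class and preferred term as follows: "The number and percentage of subjects with TEAEs, as classified by SOC and PT will be summarized". The counting rule makes these incidence proportions: "A subject reporting the same adverse event more than once is counted once and at the maximum severity". The overview table adds raw numbers of TEAEs. Protocol 7.5.1 has the same form, by treatment group: "The number and percentage of TEAEs, serious TEAEs, AEs leading to discontinuation and TEAEs related to study drug will be summarized".

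**Time at risk.** Under Protocol 5.1.1 subjects are treated "until disease progression, unacceptable toxicity, or any other discontinuation criteria are met". SAP 7.5 opens the treatment-emergent window at first dose and closes it 30 days after the last dose or at the start of subsequent treatment, whichever is earlier. Safety summaries use only data inside that window.

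**Exposure.** SAP 7.3.1 summarizes time on drug separately, descriptively and in three categories (under 3 months, 3 to under 6, 6 or more). The definition begins "Duration of exposure (defined in days as the date of last dosing - the date of first dosing + 1", so it stops at the last dose.

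Neither document plans an event rate per person-time, a time-to-first-event or cumulative-incidence analysis, or an adverse event table over a fixed window.

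**The concern.** A subject watched for longer has more chance of a first event at the same underlying rate. If enzalutamide delayed progression, its subjects would stay in the window longer and background events of advanced liver cancer would accumulate. If it were poorly tolerated, the window would be shorter and a true excess could be masked. The planned adverse event tables do not adjust for either.

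Safety is a secondary objective, and Protocol 7.1 says the sample size was set mainly to give clinical experience for designing later trials. Crude differences do get read as a drug profile. Protocol 1.2.2 describes the prostate cancer experience by listing events at least 2 percentage points more frequent than on placebo. Appendix 12.2 says that disease-related serious events may be reported to the regulator if aggregate analysis shows them more often with study drug.

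**Working it through.** **The plan's own figures.** The documents give no figure for the safety comparison and no treatment duration by arm. The only planning ratio is for survival (Protocol 7.1): "Median OS for placebo and enzalutamide are 7.0 months and 10.77 months (HR=0.65), respectively". It is internally consistent, since 7.0 / 0.65 = 10.77. It is not a ratio of treatment times.

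**Assumptions.** All are illustrative.
- The hazard λ of a first event is constant and the same in both arms, so there is no drug effect.
- Time on treatment is exponential, with mean m on placebo and m/HR on enzalutamide, where HR is the discontinuation hazard ratio. m is 2 to 4 months; HR is 0.65, 1.0 or 1.5.
- The tail is w = 30/30.4375 = 0.986 months, taken as complete.
- Arm sizes are 110 and 55: the 165 enrolled (Protocol synopsis), split 2:1.

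**Formula.** The crude proportion with an event is P(m) = 1 − exp(−λw) / (1 + λm).

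**Placebo risk 20%, m = 4.** Solving P(4) = 0.20 gives λ = 0.04805 per month, and exp(−λw) = 0.9537.
- HR 0.65: mean 4/0.65 = 6.154; P = 1 − 0.9537/1.2957 = 26.4%.
- HR 1.0: P = 20.0%.
- HR 1.5: mean 4/1.5 = 2.667; P = 1 − 0.9537/1.1281 = 15.5%.

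**Placebo risk 20%, m = 2.** λ = 0.07848 and exp(−λw) = 0.9255.
- HR 0.65: mean 3.077; P = 1 − 0.9255/1.2415 = 25.4% (25.45% before rounding).
- HR 1.5: mean 1.333; P = 1 − 0.9255/1.1046 = 16.2%.

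**Against sampling error.** SE = √(0.2 × 0.8/55 + P(1 − P)/110).

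| m (months) | HR | Enzalutamide % | Difference (points) | SE (points) | Difference / SE |
|---|---|---|---|---|---|
| 2 | 0.65 | 25.4 | +5.4 | 6.8 | 0.80 |
| 4 | 0.65 | 26.4 | +6.4 | 6.8 | 0.93 |
| 2 | 1.5 | 16.2 | −3.8 | 6.4 | 0.59 |
| 4 | 1.5 | 15.5 | −4.5 | 6.4 | 0.71 |

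For a more common event the gap can slightly exceed one standard error. With 40% on placebo, m = 4 and HR 0.65, λ = 0.12014 and P = 1 − 0.8883/1.7393 = 48.9%. The SE is √(0.4 × 0.6/55 + 0.489 × 0.511/110) = 8.1 points, and 8.9/8.1 = 1.1.

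**After the fix.** Expected person-time to first event inside the window is P/λ. At m = 4 and 20% placebo risk this is 4.163 months per subject on placebo, 5.493 on enzalutamide at HR 0.65 and 3.217 at HR 1.5. Events per 100 patient-months are then 20.0/4.163 = 4.80, 26.4/5.493 = 4.80 and 15.5/3.217 = 4.80. Under these assumptions the adjusted rates agree, as they should.

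**The case against.** **Safety is descriptive and no comparison is specified.** This largely stands. There is no test, interval or decision rule on adverse event percentages, and a crude percentage is a correct estimate of risk over treatment as given. A reader might infer that the safety comparison is biased. That goes too far, because the plan never presents the percentages as risk per unit of time. They mislead only if read that way.

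**Exposure and TEAE counts are already reported.** This stands in part. A reader might infer that the plan leaves differing follow-up invisible. It does not: SAP 7.3.1 would show an imbalance in time on drug, and dividing TEAE counts by it gives a rough rate. But the counts can include repeat events, the duration omits the tail, and subjects with a first event over time at risk cannot be rebuilt from these tables. Laboratory values and vital signs are also summarized by visit, so the gap mainly concerns adverse events.

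**The size is borrowed.** A reader might apply the survival ratio 1/0.65 = 1.54 to treatment time and drop the tail. The odds of 0.25 on placebo then become 0.25/0.65 = 0.385, so 20% turns into 27.8%. The documents do not support this as an estimate. Survival counts deaths after treatment stops, no duration assumption is stated, and the SAP includes the tail unless subsequent treatment starts first. Appendix 12.9 of the protocol reports no significant advantage on the primary endpoint, which shows neither equal nor unequal time on treatment.

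**Rates have their own weakness.** This stands. They assume a roughly constant hazard, and dividing by person-time does not remove informative stopping for toxicity or progression.

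**Conclusion.** The point holds as a gap in presentation, not as an error in an inference. The adverse event tables are unadjusted while time at risk is open-ended, and the exposure summary is neither matched to the treatment-emergent window nor linked to them.

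With the tail included and no true difference in rate, a 20% event would move to about 25-26% or about 15-16%, depending on which arm stays on treatment longer. It would not move at all if durations are equal. That is under one standard error for such an event and about one for a 40% event. These figures rest on assumed durations, exponential times and constant hazards; the effect is smaller for events that occur early. They show what could happen, not what did. No conclusion of the trial depends on this, but it could change how an imbalance in adverse events is read.

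**What to change.** In SAP 7.5.1 keep every planned table and add, by arm, exposure-adjusted incidence: subjects with a first event per 100 patient-months. Count person-time over the treatment-emergent window, from first dose to the first event or, without an event, to the end of the window. Do this for any TEAE, grade 3 or higher, serious, leading to withdrawal of treatment, and the most frequent preferred terms, with 95% confidence intervals labelled as descriptive. State that the denominator differs from the exposure duration in SAP 7.3.1 because it includes the post-dose tail.

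The cost is a few tables from dates already collected. Since the protocol already reports the primary analysis, they may have to enter as a supplementary analysis justified in the study report, which SAP section 1 allows. The downside is that the rates need a roughly constant hazard and do not correct for informative discontinuation, so they supplement the percentages and do not replace them.

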7.5.2 Clinical Laboratory Evaluation

For each quantitative laboratory parameter, summary statistics of change from baseline value by visit will be presented. The baseline laboratory value is defined as the last laboratory value collected on or prior to the first dose date of study drug.

Using the definitions provided in the NCI CTCAE, lab values will be classified as Grade 0 through 4, where possible. For each lab parameter at each scheduled collection time point, the number and percentage of subjects who have lab values within the categories defined by each of the grades will be displayed. If a subject has multiple lab values that fall into more than one NCI CTCAE grade, the highest NCI CTCAE grade will be displayed for that subject. In the event the NCI CTCAE grade is listed as > ULN or < LLN, standard laboratory normal values will be used for the purposes of comparison. These values are maintained by

the Data Management group using the New England Journal of Medicine SI Unit Conversion Guide as a reference.

It is acknowledged that data summaries based upon the standard normal laboratories may result in observations falling into different NCI CTCAE/normal/abnormal categories than those that the treating physician reports.

Shift tables will be created for each of the lab parameters after classifying by NCI CTCAE criteria. Shift from baseline to the highest NCI CTCAE grade will be presented.

Lab abnormalities will also be summarized by CTCAE Grade with number and percent, by visit and overall during the study.

Shift table for highest CTCAE grade urinalysis and urinalysis by CTCAE will not be provided.

Summary shifts of reference range changes from baseline to each treatment visit will be presented.

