Study Week/Visit	-3 to -1	1	3	5	9	13	17 + Q4 Weeks				
Study Day	-21 to -1	1	15	29	57	85	113+	N/A	≤ 7D after last dose	30D after last dose	Q30 days
Window (days)	N/A	0	+/-3	+/-3	+/-3	+/-3	+/-3	N/A	N/A	+10	+10
Informed consent	X										
Inclusion/exclusion criteria	X	X									
Return and/or dispense study drug		X	X	X	X	X	X	X [OPT]	X		
Concomitant medications ²	X	X	X	X	X	X	X	X	X	X	
Demographics, medical and disease history	X										
BCLC staging	X										
Child-Pugh classification	X										
HBV/HCV status ³	X										
Tumor assessment ⁴	X	To be performed Q8Weeks (+/- 7 D) from Day 1						X [OPT]			
Height	X										
Weight	X	X		X	X	X	X	X [OPT]	X		
Vital signs	X	X	X	X	X	X	X	X [OPT]	X		
Adverse events ⁵	X	X	X	X	X	X	X	X	X	X	
Clinical laboratory tests ⁶	X ⁷	X ⁸	X	X	X	X	X	X [OPT]	X		
Urine pregnancy test ⁹	X	X		X	X	X	X	X [OPT]	X		
Physical examination	X	X	X	X	X	X	X	X [OPT]	X		
12-lead ECG	X					X		X [OPT]	X		
ECOG PS	X	X	X	X	X	X	X	X [OPT]	X		
Alpha-fetoprotein	X	X ⁸	X	X	X	X	X	X [OPT]	X		
HBV viral load (if applicable)	X	To be done per SOC or as clinically indicated									
Pharmacokinetic sample ¹⁰			X	X	X			X [OPT]			
Tumor tissue collection ¹²		X				X					
Blood samples for PGx biobanking (optional)		X									
Survival and subsequent treatment			X		X	X	X			X	X

Footnotes appear on next page

Abbreviations: BCLC: Barcelona Clinic Liver Cancer, D: day(s), ECG: electrocardiogram, ECOG PS: Eastern Cooperative Oncology Group Performance Status, EOT: end of treatment, FSH: follicle-stimulating hormone, FU: follow-up, HBV: hepatitis B virus, HCV: hepatitis C virus, N/A: not applicable, OPT: optional, PGx: pharmacogenomics, Q: every, SOC: standard of care

1. Phone call may be conducted if subject is unable to travel. Long-term follow-up will occur for up to 2 years, until death or subject withdraws consent or final analysis.
2. Medications taken within 14 days before the Screening visit and up to the 30-day Follow-up Visit will be collected.
3. HBV/HCV status will be assessed at Screening. HBV should be assessed using an assay for hepatitis B surface antigen. HCV testing should be performed using an antiHCV antibody assay (enzyme immunoassay [EIA] or enhanced chemiluminescence immunoassay [CIA]).

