Abbreviations: ALT: alanine aminotransferase; AST: aspartate aminotransferase; NCI CTCAE: National Cancer Institute Common Toxicity Criteria for Adverse Events; TBL: total bilirubin; ULN: upper limit or normal

Note: For any Grade 3 or 4 hepatic toxicity that does not resolve within 14 days to CTCAE Grade \leq 1 (or CTCAE Grade \leq 2 if liver infiltration with tumor present), an abdominal CT scan should be performed to assess if the event is related to disease progression. Subjects with a history of viral hepatitis and an ALT or AST \geq Baseline + 4 x ULN while on treatment should have a hepatitis B and C viral loads performed per institutional guidelines to check for possible reactivation.

For Grade 4 LFTs (AST, ALT, TBL), increases related to the underlying disease or other nonstudy drug related causes, the Investigator in consultation with the Medical Monitor may consider holding study drug until values return to baseline or lower.

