7.5.2 Laboratory Assessments

Laboratory data consist of hematology, chemistry, coagulation, viral load (if applicable), pregnancy and urinalysis test results. Where applicable, NCI CTCAE version 4.03 will be used to categorize toxicity grades for the laboratory parameters. Laboratory shift tables compared to baseline results for each subsequent visit will be produced. For each laboratory parameter, the baseline laboratory value is defined as the last laboratory value collected on or prior to the first dose date of study drug.

For quantitative laboratory measurements descriptive statistics will be used to summarize results and change from baseline by treatment group and time point. Shifts relative to normal ranges from baseline to each time point during treatment period in lab tests will also be tabulated. Laboratory data will be displayed in listings.

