6.1.3 Other Efficacy Variables

6.2 Safety Variables

Safety will be assessed by evaluation of the following variables:

- Treatment-emergent adverse events (TEAEs); frequency of TEAEs by system organ class, preferred term, NCI CTCAE grade, frequency of treatment discontinuations due to AEs, severity, and relationship to study drug.
- Clinical laboratory variables (hematology, biochemistry including liver function tests, coagulation parameters and urinalysis, viral load, and pregnancy test).
- Vital signs (systolic and diastolic blood pressure and pulse rate) and body weight.
- 12-lead electrocardiogram (ECG).

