7 STATISTICAL METHODOLOGY

7.1 General Considerations

In general, all data will be summarized with descriptive statistics (number of subjects, mean, median, standard deviation (SD), minimum, and maximum) for continuous endpoints, and frequency and percentage for categorical endpoints.

For continuous variables, descriptive statistics will include the number of subjects (n), mean, standard deviation, median, minimum and maximum. When needed, the use of other percentiles (e.g. 10%, 25%, 75% and 90%) will be mentioned in the relevant section.

Frequencies and percentages will be displayed for categorical data. Percentages by categories will be based on the number of subjects with no missing data, i.e. will add up to 100%.

For time to events variables (OS, PFS and [REDACTED]), descriptive statistics will include the number of subjects (n), the number of events, the number of censored subjects, median time and 95% CI. Kaplan-Meier plots will also be generated.

Summaries based on FAS (e.g. baseline and efficacy data) will be presented, unless specifically stated otherwise. Safety analysis and other summaries based on SAF will be presented.

All data processing, summarization, and analyses will be performed using SAS® Version 9.3 or higher on Unix. Specifications for table, figures, and data listing formats can be found in the TLF specifications for this study.

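### The SAP plans no log10 change and no count of subjects with a viral-load rise, so its untransformed by-visit change summary can obscure a reactivation signal

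*SAP*

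**What the plan says.** SAP 6.2 lists among the clinical laboratory variables "coagulation parameters and urinalysis, viral load, and pregnancy test". SAP 7.5.2 then sets one numeric rule for all of them: "For each quantitative laboratory parameter, summary statistics of change from baseline value by visit will be presented". SAP 7.1 defines such summaries: "descriptive statistics will include the number of subjects (n), mean, standard deviation, median, minimum and maximum". SAP 7.10.1 and 7.10.3 keep all values in, and the only rule for values below quantification (SAP 7.6) is for drug concentrations.

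SAP 7.5.2 also plans CTCAE grading, under which "lab values will be classified as Grade 0 through 4, where possible", and reference-range shifts: "Summary shifts of reference range changes from baseline to each treatment visit will be presented". Protocol 7.5.2 adds summaries of the values themselves ("descriptive statistics will be used to summarize results and change from baseline by treatment group and time point") and subject-level listings.

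The protocol gives viral load a specific purpose. Under the dose modification table in Protocol 5.1.2.1, subjects with a history of viral hepatitis and an on-treatment ALT or AST of at least baseline + 4 x ULN "should have a hepatitis B and C viral loads performed per institutional guidelines to check for possible reactivation". In the schedule of assessments (Protocol Table 1), HBV viral load is taken at Screening and thereafter is "To be done per SOC or as clinically indicated".

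**The concern.** Reactivation is a proportional rise from the subject's own starting level. An untransformed difference measures something else: the same fold change counts for far more in a subject who starts high. Where starting levels differ by several powers of ten, the mean, SD, minimum and maximum of the raw change mostly describe fluctuation in the highest-titre subjects. The median escapes that, but it barely responds to a rise confined to a minority.

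The by-visit layout adds a second problem on any scale. Since sampling after Screening follows local practice or clinical need, the subjects contributing at one visit are not those contributing at the next, and some are tested because something was already suspected.

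At stake is whether a reader of the study report can see if more subjects on enzalutamide than on placebo had a viral-load rise. The question is a natural one here. The trial enrols in Asia, and Protocol 1.1 names hepatitis B as the most common etiology in East Asia.

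**Working it through.** The documents state no viral-load figure, number of HBV subjects or titre distribution, so there is no plan figure to reproduce. All titres below are assumptions.

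**Step 1: single subjects.**
- A 1000-fold rise from 100 to 100,000: 10^5 - 10^2 = 99,900.
- A 0.2 log10 fluctuation at 10,000,000: 10^7 x (10^0.2 - 1) = 5,848,932.
- Ratio: 5,848,932 / 99,900 = 58.5. On the raw scale the minor fluctuation is about 58 times the 3-log rise.

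**Step 2: a group of 30.** Assume 25 subjects stable at 20 IU/mL, 2 at 10,000,000, and 3 who rise from 20 to 20,000 (each +19,980, or +3 log10).
- If the two high-titre subjects fall 0.2 log10 (each -3,690,427), the raw mean is (3 x 19,980 - 2 x 3,690,427) / 30 = -244,030. Without the three risers it is -2 x 3,690,427 / 27 = -273,365. Both show a fall.
- If those two instead rise 0.2 log10, the raw mean is (59,940 + 11,697,864) / 30 = +391,927, against +433,254 without the risers. The maximum, 5,848,932, belongs to a high-titre subject.
- The raw median is 0 in every case, because 3 of 30 is a minority.
- The log10 mean in the falling case is (3 x 3 - 2 x 0.2) / 30 = +0.29, against -0.01 without the risers. The count with a rise of at least 1 log10 is 3/30 (10%) whatever the two high-titre subjects do.
- With no high-titre subjects (28 stable, 3 risers), the raw mean does move: 59,940 / 31 = +1,934.

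Adding measurement error of 0.1 to 0.3 log10 SD to the 30-subject example, the raw mean is positive in 50% to 55% of runs when the high titre is 10^6 or more, in 69% to 91% at 10^5, and the log10 mean in 100%.

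**Step 3: two arms.** Assume 20, 40 or 80 HBV subjects at 2:1 (14/6, 27/13, 54/26), 0.3 log10 noise, one post-baseline value each, and a true 2 log10 rise in 2, 3 or 5 enzalutamide subjects and no placebo subject. The outcomes are how often the raw mean change is higher on placebo, and how often the largest raw change belongs to a subject without reactivation.

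| Baseline log10 mean, SD | Raw mean in wrong direction | Largest change not a riser |
|---|---|---|
| 1.5, 0.5 | 0.0% to 0.4% | 0.1% to 0.4% |
| 1.5, 0.75 | 1% to 2% | about 3% |
| 2, 1 | 5% to 8% | 9% to 12% |
| 2, 1.5; 3, 2; 4, 2 | about 17% to 27% | about 29% to 46% |

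In the settings of the last row, the log10 mean points the wrong way in at most about 3% of trials. The raw median change is higher on enzalutamide in only 60% to 66%. A count of rises of at least 1 log10 shows an excess of two or more on enzalutamide in 97% or more.

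**Step 4: the other displays.**
- Reference-range shifts: a subject already above the range at baseline shows no shift, however large the rise.
- CTCAE grades: applied only where possible, and the documents give no grade for viral load.
- Result summaries: by arm and time point, so they do not show within-subject rises and share the scale problem.
- Listings: show each rise, but give no comparison by arm.
- LFT threshold counts (SAP 7.5.2.1): cover the hepatic trigger, not its viral cause.
- AE tables: compare arms, but depend on the investigator reporting the event.

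**The case against.** The strongest reply is that the plan is not blind to reactivation. A reader might infer that viral load is summarised solely as raw change, or that a reactivation would surface only through an AE report. The documents support neither. SAP 7.5.2 and Protocol 7.5.2 plan shifts, grades where possible, result summaries and listings, and SAP 7.5.2.1 counts potentially clinically significant liver tests. With perhaps a few dozen HBV subjects tested irregularly, a listing would show a rise from 100 to 100,000 directly. This stands, but a listing is not a prespecified comparison of the arms.

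Second, the untransformed scale is inferred from silence: no unit or scale is stated for viral load, samples go to local laboratories, and SAP 7.1 leaves formats to table specifications that are not in these documents. This stands as a caveat. The remedy is the same, since the SAP is where the scale should be fixed.

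Third, the effect may be negligible. Protocol 5.1.3 says subjects with viral etiology should be on stable antiviral doses at entry where the investigator sees benefit, which makes low, narrow titres plausible. The first rows of the table show that the raw mean then seldom misleads. This stands, and it is why no single error rate can be attached to the plan.

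Finally, no test, decision rule or stopping rule in the documents uses viral load. That limits the weight of the point but does not remove it.

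**Conclusion.** The point holds as a gap in a descriptive safety analysis. Followed as written, SAP 7.5.2 applies an untransformed by-visit change to a measure that can span many powers of ten and is sampled selectively. Nothing else in the readable text compares the arms on measured viral-load rises.

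The size is conditional. On assumed inputs the raw mean favours the wrong arm in about 0% of trials with low, narrow titres, 5% to 8% at log10 mean 2 and SD 1, and up to about 27% with wide or high titres. Quoting the upper figures alone would be one-sided. All of these also assume one post-baseline value for every subject, which the selective sampling contradicts; the favourable figures for the log10 mean and the count rest on the same assumption.

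The point covers HCV as well as HBV, because the protocol's reactivation check names both. It does not touch the overall survival analysis.

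**What to change.** In SAP 7.5.2, replace the by-visit change summary for HBV viral load, and for HCV viral load where collected, with a table giving per arm:

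- each subject's maximum log10 change from baseline within the treatment-emergent period, summarised descriptively;
- the number and percentage of subjects at or above prespecified log10 rises. Cut-offs such as 1 and 2 log10 are examples of reporting thresholds. The documents give none, the sponsor should justify its choice, and they carry no dosing or clinical consequence;
- the number of subjects tested, with subjects having a baseline and at least one post-baseline value as denominator.

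State how values below each local assay's limit are handled, since limits may differ between laboratories. List the subjects with a rise alongside concurrent ALT and antiviral use. Protocol Table 1 names only HBV viral load at Screening, so HCV values may lack a baseline; those should be listed rather than dropped.

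The cost is SAP wording, one table and one listing, from data already collected. The limitation is that a maximum-change summary still depends on who was tested and how often, which is why the number tested must appear beside it.
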